# 8.3.3 Definition of Dose-Limiting Toxicity

A dose-limiting toxicity (DLT) is defined as a clinically significant AEs or abnormal laboratory value assessed as unrelated to disease progression, intercurrent illness or concomitant medications, occurring after at least one dose of investigational product during the DLT assessment period (see Section 3.1.1) and meeting any of the following criteria:

- CTCAE Grade 3 AST (SGOT) or ALT (SGPT) or bilirubin for ≥7 days
- CTCAE Grade 4 AST (SGOT) or ALT (SGPT) of any duration
- CTCAE Grade 3 or higher febrile neutropenia, neutropenia or thrombocytopenia
- CTCAE Grade 4 (life-threatening) vomiting or diarrhoea, regardless of response to management.
- CTCAE Grade 4 electrolyte abnormalities, regardless of response to management.
- All other, AEs CTCAE Grade 4.
- All other AEs Grade 3 with the following exceptions: Transient (less than 24 hours within injection time) nausea and vomiting, investigational product-related fever, electrolyte abnormalities (including K, Na, Cl, HCO3, Mg, Ca) anorexia and alopecia.

To be considered a DLT, the toxicity should be assessed as at least possibly related to the investigational product.

An AE must be clinically significant to be defined as a DLT (e.g. nausea and vomiting, investigational product-related fever, electrolyte abnormalities (including K, Na, Cl, HCO3, Mg, Ca) that are ≤ Grade 3 will not constitute a DLT).

V2		PRIVILEGED & CONFIDENTIAL
Investigational Product: AGI-134	A Phase I/IIa, multicentre, two-parts, open label study designed to evaluate the safety and tolerability of escalating	Protocol No. AGI-134.FIM.101
Phase: I/IIa		Version 6.1 31 May 2021

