	During the first cycle of treatment for each dose, a subject that experiences a dose-limiting toxicity (DLT) or an adverse event (AE) of moderate or high severity, assessed as related to AGI-134 and as clinically significant, will trigger an expansion of the dose level group to a total of three subjects, and the study will continue in a conventional "3+3" design. If the AE is a DLT, an expansion of the dose level to a total of 6 subjects prior to escalation to the next dose level will be triggered and will be performed in a stepwise manner, dosing an additional two subjects in the first dose expansion step, followed by an additional three subjects that would be dosed only if no second DLT occurs.

20		PRIVILEGED & CONFIDENTIAL
Investigational Product: AGI-134		Protocol No. AGI-134.FIM.101
Phase: I/IIa		Version 6.1 31 May 2021

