AEs severity (Table 4) will be recorded and graded according to the latest version of the NCI-CTCAE (currently version 5.0) and coded into the database according to the latest version of MedDRA (currently version 24.0).

Table 4: Severity of Adverse Events According to CTCAE (Version 5.0)

Grade	Description
0	No AE or within normal limits
1	Mild; asymptomatic or mild symptoms; clinical or diagnostic observations only; intervention not indicated.
2	Moderate; minimal, local or non-invasive intervention indicated; limiting age-appropriate instrumental Activities of Daily Living (ADL)
3	Severe or medically significant but not immediately life-threatening; hospitalisation or prolongation of hospitalisation indicated; disabling; limiting self-care ADL
4	Life-threatening consequences; urgent intervention indicated
5	Death related to AE

A semi-colon indicates 'or' within the description of the grade.

A single dash (-) indicates a grade is not available

The following definitions should be used for toxicities/AEs that are not defined in the CTCAE:

Protocol AGI-134.FIM.101 CONFIDENTIAL Page 65 of 108

20		PRIVILEGED & CONFIDENTIAL
Investigational Product: AGI-134		Protocol No. AGI-134.FIM.101
Phase: I/IIa		Version 6.1 31 May 2021

- Mild (Grade 1): The AE is noticeable to the subject but does not interfere with routine activity, no medical intervention is required;
- Moderate (Grade 2): The AE interferes with routine activity but responds to symptomatic therapy or rest;
- Severe (Grade 3): The AE significantly limits the subject's ability to perform routine activities despite symptomatic therapy;
- Life-threatening (Grade 4): The subject is at immediate risk of death.

The PI will document his opinion of the relationship of the AE to treatment with investigational product using the criteria outlined in Table 5.

Outcome to Date are classified as follows:

- Recovered: The subject has fully recovered from the AE with no observable residual effects
- Recovered with sequelae: The subject has recovered from the AE with observable residual effects
- Improved: The subject status has improved but is not fully recovered
- Ongoing: AE is not recovered
- Fatal
- Unknown

AEs will be coded by Data Management using the latest version of MedDRA (currently version 24.0) AE dictionary.

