### 8.3.1 Part 1 – Accelerated Dose Escalation of AGI-134

At any given dose, if one subject presents with a dose-limiting toxicity (DLT) or an event of moderate or higher severity assessed as related to AGI-134 and as clinically significant during the first cycle of treatment, the group of subjects will be expanded and the study will continue in a conventional "3+3" design. The expansion after an event of moderate severity will be to a total of 3 subjects and the expansion after a DLT will be to a total of 6 subjects, recruited in a stepwise manner of 3+3. Moderate injection site reactions are expected events with any injectable drug, as are moderate drug administration-related fever, nausea and vomiting. These will therefore will not be considered as a trigger for conversion to a "3+3" design. If the group of subjects was expanded due to a clinically significant related event that is not a DLT, and this expanded group, i.e. 3 subjects, showed no DLT events, then the study will continue to the next dose level enrolling 3 subjects.

If 1 out of 3 subjects presented with a DLT in the expanded cohort, a group of additional 3 subjects will be treated at the same dose level. If no more DLTs are reported at that dose, i.e. only 1 out of a total of 6 subjects has developed a DLT, the dose escalation will continue to the next level. At any given dose, if 2 or more out of 6 subjects experience a DLT, that dose level will be considered as the DLT dose. In such a case, 3 more subjects will be administered at the previous dose level, if there are less than 6 subjects already treated at that dose. MTD is defined as the highest dose level in which 6 subjects have been administered with and less than 2 instances of DLT.

When the first subject in each dose completes the first cycle of treatment, (each Cycle is 3 weeks long), the safety and tolerability will be assessed by a Safety Committee to decide whether to escalate the dose or to expand the group of subjects. When the MTD is reached or the 200 mg dose is found to be safe, whichever comes first, it will be defined as the RP2D and the study will continue to Part 2.

After completion of the first treatment cycle, subjects in Part 1 of the study will continue receiving intratumoural injection at the dose determined at Screening for 3 additional cycles. No intra-subject escalation will be allowed. The treatment regimen is one dose per cycle of AGI-134 every three weeks for up to 4 cycles.

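### The DLT definition in Section 8.3.3 reaches Grade 5 only through its cytopenia criterion, so read literally a related Cycle 1 death from another cause need not count as a DLT

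*Combined protocol and SAP*

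**What the plan says.** Section 8.3.3 requires an event to satisfy at least one of seven listed criteria, to occur in the DLT window, to be clinically significant, to be at least possibly related to the product, and not to be explained by progression, intercurrent illness or concomitant medication. One criterion is open at the top: "CTCAE Grade 3 or higher febrile neutropenia, neutropenia or thrombocytopenia". The others name Grade 3 or Grade 4 and stop there, including the catch-all "All other, AEs CTCAE Grade 4".

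Table 4 in Section 7.1 treats Grade 4 (life-threatening) and Grade 5 ("Death related to AE") as different grades. For events that CTCAE does not define, the same section gives a separate scale whose top category is "Life-threatening (Grade 4): The subject is at immediate risk of death".

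In Part 1 a DLT expands the dose group to 6. In the synopsis, a moderate or worse event "assessed as related to AGI-134 and as clinically significant, will trigger an expansion of the dose level group to a total of three subjects". Section 8.3.1 is narrower: "The expansion after an event of moderate severity will be to a total of 3 subjects". It gives no group size for a worse event that is not a DLT. It then says that if a group expanded for a non-DLT event "showed no DLT events, then the study will continue to the next dose level enrolling 3 subjects". Two or more DLTs in 6 make the level the DLT dose, and the MTD is the highest level with 6 treated and fewer than two DLTs.

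**The concern.** The DLT count drives expansion, the DLT dose and the MTD, and the MTD is part of the primary endpoint (Section 2.2.1). A rule that counts a life-threatening related event but not a fatal one gives the wrong answer for the worst outcome.

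The case is not fanciful. Section 5.7 requires treatment for hypersensitivity reactions to be at hand at every injection, and Table 2 explains anti-Gal IgE screening by the risk of acute hypersensitivity. A fatal reaction after the first injection would fall under the catch-all criteria, which list only Grades 3 and 4.

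The same definition feeds two Part 2 rules: the deep-lesion expansion (Sections 3.1 and 8.3.2) and the accrual stop for a DLT-type event above 30% (Section 3.1.1).

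**Working it through.** **Step 1: apply each criterion literally (Section 8.3.3 against Table 4).**

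| Event type | Grade 3 | Grade 4 | Grade 5 |
|---|---|---|---|
| Febrile neutropenia, neutropenia, thrombocytopenia | DLT | DLT | DLT |
| AST/ALT | DLT if 7 days or longer | DLT | not listed |
| Vomiting, diarrhoea | catch-all, with exceptions | DLT | not listed |
| Electrolytes | excepted | DLT | not listed |
| All other AEs | DLT, with exceptions | DLT | not listed |

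Nothing elsewhere in the protocol adds death or Grade 5 to the definition.

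**Step 2: the plan's own figure.** Section 8.1 gives a Part 1 maximum of 24: 4 dose groups × 6 subjects = 24. It reproduces and is not in dispute.

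**Step 3: what the written rule does after such a death.** Illustration only. Subject 1 has a related Grade 5 event that is not a listed cytopenia. Every other subject independently has DLT probability p. The documents give no rate, so p = 0.10, 0.20 and 0.30 are assumed. Committee discretion and the general stop in Section 3.1.1 are ignored.

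- **A. Not counted, subject kept in the group of 3.** Escalate if neither of the next two has a DLT, or if exactly one does and the further three do not: (1−p)² + 2p(1−p)·(1−p)³.
  - p = 0.10: 0.810 + 0.180 × 0.729 = 0.941
  - p = 0.20: 0.640 + 0.320 × 0.512 = 0.804
  - p = 0.30: 0.490 + 0.420 × 0.343 = 0.634
- **B. Not counted, subject replaced** (one reading of Section 4.5). Three evaluable subjects, then three more if exactly one has a DLT: (1−p)³ + 3p(1−p)²·(1−p)³.
  - p = 0.10: 0.729 + 0.243 × 0.729 = 0.906
  - p = 0.20: 0.512 + 0.384 × 0.512 = 0.709
  - p = 0.30: 0.343 + 0.441 × 0.343 = 0.494
- **C. Counted as a DLT.** The group goes to 6 and escalation needs no DLT in the other five: (1−p)⁵ = 0.590, 0.328, 0.168.

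| p | A | B | C | A−C | B−C |
|---|---|---|---|---|---|
| 0.10 | 0.941 | 0.906 | 0.590 | 0.351 | 0.316 |
| 0.20 | 0.804 | 0.709 | 0.328 | 0.476 | 0.381 |
| 0.30 | 0.634 | 0.494 | 0.168 | 0.466 | 0.326 |

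**Step 4: without conditioning on a death.** In a conventional 3+3 group the escalation probability is (1−r)³ + 3r(1−r)⁵, where r is the rate of counted events. Take a non-fatal DLT rate of 0.20 and a related fatal rate of 0.05 or 0.10, both assumed. As written, r = 0.20 and the probability is 0.709. With deaths counted, r = 0.25 or 0.30 and it is 0.600 or 0.494. The gaps are 0.109 and 0.214. With non-fatal rates of 0.10 and 0.30 the gaps are 0.092 and 0.098 at the lower fatal rate, and 0.198 and 0.185 at the higher.

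**Step 5: Part 2.** One event exceeds 30% only while three or fewer subjects are counted (1/3 = 33%, 1/4 = 25%). At 35 subjects it takes 11 (11/35 = 31.4%; 10/35 = 28.6%). Two or more deep-lesion DLTs lead only to a committee risk-benefit review. The Part 2 effect is small.

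**The case against.** The strongest reply is that the gap is narrow and the trial is protected anyway.

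*Narrow.* Section 8.3.3 asks whether an event meets any criterion and does not say that the final grade decides. Section 8.2.2 specifies worst grade for the summary tables, so the protocol can say so when it means it. A toxicity recorded as Grade 4, or as a non-excepted Grade 3, before it became fatal may already count. A fatal event outside CTCAE has no grade above 4 to move into. Both points stand, and they shrink the gap. What remains is a related, CTCAE-defined death that is not a listed cytopenia and is recorded only as Grade 5. A rapid fatal reaction could be exactly that.

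*Protected.* Related events of moderate or higher grade that are clinically significant require sponsor contact within 24 hours (Section 8.3). Fatal events are reported at once (Section 7.2.5.1). Each dose level is "assessed by a Safety Committee to decide whether to escalate the dose or to expand the group of subjects", and Section 3.1.1 ends the study for unacceptable risk. These would very likely act. They are reporting or judgement steps, however, and none changes the count. The committee's standing members are the study PI and two sponsor staff (Section 3.1), which is a reason to prefer an explicit rule.

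*Inflated size.* The Step 3 gaps condition on a rare event and switch off discretion, so they do not forecast how the trial would behave. That is fair. Case B is also doubtful, because the paragraph in Section 4.5 on discontinuation during the DLT period allows replacement for reasons other than safety. The expansion to 3 rests on the synopsis and on the non-DLT sentence in Section 8.3.1, since the explicit size there is tied to moderate events.

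*One edit would do.* Opening the catch-all may be enough, and the documents do not show that every listed laboratory term has a Grade 5. But vomiting, diarrhoea, electrolytes and AST/ALT are named separately, so whether the catch-all reaches their fatal forms would be arguable. The extra edits remove that doubt at no cost.

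**Conclusion.** The concern holds: the definition is wrong as written. A related Cycle 1 death recorded as Grade 5, other than from a listed cytopenia, falls outside the DLT count that sets the DLT dose and the MTD. Given such a death in the first subject, the written rule permits escalation 0.35 to 0.48 more often than if the death counted, or 0.32 to 0.38 more often if the subject is replaced. This rests on assumed DLT probabilities of 0.10 to 0.30 in the other subjects and on no intervention by the committee. Without that conditioning the gap is roughly 0.09 to 0.21 for assumed related-death rates of 5% to 10%. The intent is almost certainly to count such deaths and the backstops are substantial, so this is a correction that should be made rather than a flaw that invalidates the design.

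**What to change.** Edit Section 8.3.3 only. Change the Grade 4 catch-all to *All other AEs of CTCAE Grade 4 or higher*, and add *or higher* to the Grade 4 criteria for AST/ALT, vomiting or diarrhoea, and electrolyte abnormalities. Extend the life-threatening gloss in the vomiting/diarrhoea criterion to fatal events so that it does not undercut the change. Leave the opening exclusions and the relatedness sentence as they are, so that deaths from progression, intercurrent illness or concomitant medication stay outside the count.

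The cost is a few words in four criteria. No new data are needed, the sample size does not change, and the other sections inherit the correction through the defined term.

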### 8.3.2 Part 2 - AGI-134 at the RP2D

Safety interim analyses are planned after 3 subjects with deep injectable lesions have completed the first cycle with AGI-134 (i.e. Cycle 1 - Day 1 through to Cycle - Day 21). Sites will be required to contact the Sponsor within 24 hrs if a subject present with a DLT during the DLT assessment period (see Section 3.1.1).

During Part 2, 3 subjects will be evaluated after one cycle of injection into deep lesions. If one or more of the subjects experiences DLTs, a new assessment will be done after the additional 3 subjects with deep lesions injected are enrolled and treated (total 6 subjects). If no new DLTs are reported, the recruitment will continue as planned. If 2 or more subjects presented a DLT, the SC will assess the risk vs. benefit of the treatment and recommend whether or not the dose of AGI-134 should be reduced and/or the treatment schedule be changed (see Section 8.3).

Following the assessment of the first 3 patients with deep lesion injected or 6 patients if expansion is needed, the safety data will be evaluated by the Safety Committee. Evaluation by

agalin A subsidiary of Bio	nnune DLINERX	PRIVILEGED & CONFIDENTIAL
Investigational Product: AGI-134		Protocol No. AGI-134.FIM.101
Phase: I/IIa		Version 6.1 31 May 2021

the Safety Committee will be conducted every 6 months to review ongoing safety data, until the last patient last visit (LPLV).

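### Section 8.3.3 gives two incompatible rules for Grade 3 nausea or vomiting lasting 24 hours or more, so the same data can give opposite dose decisions

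*Combined protocol and SAP*

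**What the plan says.** Section 8.3.3 lists the DLT criteria. After the organ-specific and Grade 4 items comes a Grade 3 catch-all: "All other AEs Grade 3 with the following exceptions: Transient (less than 24 hours within injection time) nausea and vomiting". The list of exceptions continues with product-related fever, electrolyte abnormalities, anorexia and alopecia. The section closes with a general condition: "An AE must be clinically significant to be defined as a DLT (e.g. nausea and vomiting, investigational product-related fever". Its parenthesis goes on to electrolyte abnormalities and concludes that, at or below that level, "Grade 3 will not constitute a DLT". It states no duration.

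The DLT count feeds these rules:

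- **Expansion, Part 1.** In the Synopsis, a DLT or a related, clinically significant event of at least moderate severity in the first cycle "will trigger an expansion of the dose level group to a total of three subjects". A DLT takes the level to six in steps, with two more subjects, "followed by an additional three subjects that would be dosed only if no second DLT occurs".
- **Carve-out from the trigger.** Section 8.3.1: "Moderate injection site reactions are expected events with any injectable drug, as are moderate drug administration-related fever, nausea and vomiting". These do not convert the study to 3+3. The carve-out covers moderate events only.
- **MTD.** Section 8.3.1: "MTD is defined as the highest dose level in which 6 subjects have been administered with and less than 2 instances of DLT". Two or more DLTs in six make a level the DLT dose.
- **Part 2.** Under Section 8.3.2, a DLT in one or more of the first three deep-lesion subjects leads to three more subjects and a new assessment. Then: "If 2 or more subjects presented a DLT, the SC will assess the risk vs. benefit of the treatment". Sections 3.1.1 and 8.3 also stop accrual if a specific event meeting the DLT definition exceeds 30%.

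Section 4.5 has two replacement rules. One paragraph requires replacement of anyone withdrawn before the DLT period ends, whatever the reason. The next makes replacement optional and limits it to non-safety reasons. It also takes subjects who leave for progression out of the DLT assessment, without an exception for a DLT that has already occurred.

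**The concern.** The MTD and RP2D are part of the primary endpoint, and a 3+3 decision can turn on a single event. If one class of event is a DLT under one sentence and not under another, two committees applying the protocol faithfully to the same subjects can reach opposite decisions. The disputed class is narrow: Grade 3 nausea or vomiting, related to AGI-134, clinically significant, lasting 24 hours or more, within Cycle 1 Days 1 to 21. Grade 4 vomiting is a DLT either way. In a first-in-human study, a choice made after the event is seen also makes the reported MTD hard to defend. The Part 2 rules use the same definition, so the problem remains even if Part 1 is complete.

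**Working it through.** **The plan's own figure.** Section 8.1 gives a Part 1 maximum of 24: 4 dose levels × 6 subjects = 24. It reproduces and is not affected.

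**The two rules applied to the same data.** No event rate is needed. A disputed event is related, clinically significant Grade 3 vomiting lasting 36 hours.

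| Data | Grade 3 criterion | Closing sentence |
|---|---|---|
| 6 subjects: 1 undisputed DLT, 1 disputed event | 2/6, DLT dose | 1/6, escalate |
| 3-subject cohort: 2 disputed events | Threshold of 2 already reached, DLT dose | 0/3, escalate |
| First subject at a level: disputed event | DLT, expand stepwise to 6 | Non-DLT event, expand to 3 |
| First 3 deep-lesion subjects in Part 2: 1 or more disputed events | 3 more subjects and a new assessment; risk/benefit and dose review if 2 or more have a DLT | No DLT, recruitment continues |
| Part 2, same event in 11 of 35 (31%) | Meets the definition and exceeds 30%, accrual stops | Never meets the definition, no stop |

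The last row takes the planned Part 2 size of about 35 as the denominator, which the protocol does not specify.

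**Conditional illustration.** Suppose the first subject at a level has a disputed event and every other subject has an undisputed DLT with probability p (assumed).

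- Grade 3 criterion: none of the next 5 may have a DLT, so P(pass) = (1−p)^5. With p = 0.20 this is 0.33; with p = 0.33 it is 0.14.
- Closing sentence: neither of 2 added subjects has a DLT, or exactly 1 does and the next 3 have none, so P(pass) = (1−p)² + 2p(1−p)^4. With p = 0.20 this is 0.64 + 0.16 = 0.80; with p = 0.33 it is 0.45 + 0.13 = 0.58.

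**Unconditional illustration.** Let p be the DLT rate with disputed events counted, s the share of those DLTs that are disputed, and r = p(1−s) the rate left under the closing sentence. Both p and s are assumed. Under the closing sentence a disputed event in a single-subject level expands it to 3; expansions for other non-DLT events are ignored.

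- Single-subject level: P(pass) = (1−p) + ps[(1−r)² + 2r(1−r)^4] + r(1−r)^5
- 3-subject cohort: P(pass) = (1−r)³ + 3r(1−r)^5

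Setting s = 0 gives the result under the Grade 3 criterion.

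| p | Single: s = 0 | s = 0.10 | s = 0.25 | Cohort: s = 0 | s = 0.10 | s = 0.25 |
|---|---|---|---|---|---|---|
| 0.20 | 0.87 | 0.88 | 0.91 | 0.71 | 0.75 | 0.81 |
| 0.33 | 0.71 | 0.74 | 0.79 | 0.43 | 0.50 | 0.61 |
| 0.50 | 0.52 | 0.54 | 0.60 | 0.17 | 0.23 | 0.35 |

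**The case against.** The best defence is that the closing sentence lays down only one rule, clinical significance, and that its parenthesis is an abbreviated example of the exceptions just listed. A specific criterion with a time limit would then prevail, and 36-hour Grade 3 vomiting would be a DLT. That may be the intent. But the parenthesis states an outcome for every such event up to Grade 3, and if it is followed the 24-hour limit does nothing. The separate Grade 4 vomiting criterion points the other way on intent. The defence shows how to repair the text, not that the text is consistent.

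It is also fair that the Safety Committee decides on escalation, that significant related events reach the sponsor within 24 hours, and that Section 3.1.1 allows termination for unacceptable risk. These limit harm, but the committee still has to apply this definition. The probability figures are indeed illustrations: in the single-subject phase, where Part 1 starts, the shift at s = 0.10 is only 2 to 3 percentage points, and the conditional contrast is not an operating characteristic of the design.

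Four stronger readings are not supported:

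- **A disputed event in a single subject triggers no expansion under the closing sentence.** The carve-out stops at moderate severity, so a related Grade 3 event judged clinically significant still expands the level to three.
- **Two DLTs in the first three deep-lesion subjects lead straight to dose review.** The rule for one or more DLTs adds three subjects before the new assessment.
- **A replaced subject's DLT is dropped.** No text says so. Section 4.5 keeps all data in the safety cohort assessment, and Section 8.3 keeps dropouts in the relevant analyses.
- **A fatal toxicity would be ignored because the general catch-all names only Grade 4.** This is a drafting slip of small reach, given committee review and the termination clause.

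**Conclusion.** The contradiction is real and should be fixed. It follows from the text alone: for Grade 3 nausea or vomiting of 24 hours or more, Section 8.3.3 supports both answers, and the answers lead to opposite escalation decisions, different expansion sizes and different Part 2 actions. How often this would matter cannot be stated, because neither the DLT rate nor the disputed share is in the documents. Over the assumed ranges, the chance of passing a dose rises by about 2 to 8 percentage points in the single-subject phase and 4 to 18 in a 3-subject cohort.

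Two uncertainties remain within the Grade 3 criterion. The 24 hours could mean duration or time since injection; the working above takes it as duration. It is also unclear whether *transient* governs fever and electrolyte abnormalities. If it does, the same conflict covers those events, because the closing sentence names them too.

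Section 4.5 is a secondary point. Its rules conflict on whether replacement is obligatory and on whether safety withdrawals are included, and no size is claimed for it.

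**What to change.** - **Section 8.3.3, closing sentence.** Put the same limit of less than 24 hours on nausea and vomiting, or delete the parenthesis so that the Grade 3 criterion governs.
- **Section 8.3.3, Grade 3 criterion.** Say whether the 24 hours is duration or time since injection, and whether *transient* also applies to product-related fever and electrolyte abnormalities.
- **Section 4.5.** Keep one rule. A treated subject with a DLT is always counted and not replaced, even if the subject later leaves for progression. Only subjects who leave the DLT period without a DLT and for non-safety reasons, progression included, are replaced.
- **Optional.** Extend the general Grade 4 catch-all to Grade 5.

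The cost is a wording amendment, with no extra subjects, visits or procedures.
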